15.9 Adaptive Study Design

The study will employ an adaptive design with potential sample size adjustment based on the proportion of discordance from the interim analysis. This study will enroll approximately 350 subjects to initially randomize and treat 300 subjects (that could potentially increase to approximately 580 subjects enrolled and 500 subjects randomized). Based on the calculation from the interim analysis an additional 200 subjects may be randomized and treated thus the study will randomize and treat a total sample size in the range of 300 to 500 subjects. Any additional sample size will be added in blocks of 50 in order to prevent any back-calculation of the interim study results. For example in the event an additional 30 subjects are needed, a total of 50 will be added to the study.

15.10 Sample Size Justification

The rates of success for the primary endpoint are assumed to be 83% and 75% for the CRS and standard manual technique arms respectively. These assumptions are based on data from the AnalyzOR Retrospective Data Exploration Study (Data on File).

An estimate of the discordance in outcome between eyes is not known; however it's estimated that discordance will be in the range 8% to 33%. For an initial sample size calculation, the midpoint value of this range, 21%, will be assumed. Based on these assumptions 267 subjects, treated contralaterally, are required to provide 90% power to reject the null hypothesis for a one sided McNemars test at the 5% level using the approximation from Miettinen (Miettinen 1968). If the proportion of discordance is 33% and all other assumptions stay the same a sample of 433 subjects is needed.

The initially planned sample size of 267 is inflated to allow for up to 10% drop out; this inflation yields a sample size of 300 subjects. Inflation of the sample size of 433 to allow for up to 10 % drop out yields a sample size of 485; the sample size of 500 is selected so that the maximum sample size will be divisible by the block size of 50.

16 ADMINISTRATIVE PROCEDURES

16.1 Regulatory and Ethical Compliance

This clinical study will be conducted in accordance with the principles of the Declaration of Helsinki, and in compliance with International Organization for Standardization (ISO) 14155:2011 Clinical investigation of medical devices for human subjects – GCP, CFR, and laws and regulations of foreign countries, whichever affords greater protection to subjects. The study will also be conducted in accordance with the Standard Operating Procedures (SOPs) of Alcon and Contract Research Organizations participating in the conduct of the clinical study, and all other applicable regulations. The Investigator and all clinical study staff will conduct the clinical study in compliance with this protocol. The Investigator will ensure that all personnel involved in the conduct of the clinical study are qualified to perform their assigned duties through relevant education, training, and experience.

16.2 Informed Consent Procedures

Voluntary informed consent must be obtained from every subject prior to the initiation of any Screening or other clinical study-related procedures. The Investigator must have a defined process for obtaining consent. Specifically, the Investigator, or designee, must explain the clinical study to each potential subject and the subject must indicate voluntary consent by signing and dating the approved informed consent form. The subject must be provided an opportunity to ask questions of the Investigator, and if required by local regulation, other qualified personnel. The Investigator must provide the subject with a copy of the consent form written in a language the subject understands. The consent document must meet all applicable local laws and will provide subjects with information regarding the purpose, procedures, requirements, and restrictions of the clinical study, along with any known risks and potential benefits associated with the investigational product, the available compensation, and the established provisions for maintaining confidentiality of personal, protected health information. Subjects will be told about the voluntary nature of participation in the clinical study and will be provided with contact information for the appropriate individuals should questions or concerns arise during the clinical study. The subject will also be told that their records may be accessed by appropriate authorities and Sponsor-designated personnel. The

Investigator must keep the original, signed copy of the consent and must provide a duplicate copy to each subject.

16.3 Responsibilities of the Investigator and IRB/IEC

Before clinical study initiation, this protocol, the informed consent form (ICF) (and assent form, if applicable), any other written information provided to subject, and any advertisements planned for subject recruitment must be approved by an IRB/IEC. A master list of IRBs/IECs for this clinical study can be found in the Trial Master File. The Investigator must provide documentation of IRB/IEC approval to the Sponsor. The approval must be dated and must identify the applicable protocol, amendments (if any), informed consent form, assent form (if any), all applicable recruiting materials, written information for subjects, and subject compensation programs. The IRB/IEC must be provided with a copy of the Directions for Use, any periodic safety updates, and all other information as required by local regulation and/or the IRB/IEC. At the end of the clinical study or in the case of early termination, the Investigator will notify the IRB/IEC of the clinical study's final status. Finally, the Investigator will report to the IRB/IEC on the progress of the clinical study at intervals stipulated by the IRB/IEC.

16.4 Sponsor and Monitoring Responsibilities

The Sponsor will designate a monitor to conduct the appropriate site visits at the appropriate intervals. The clinical study will be monitored to ensure that the rights and wellbeing of the subjects are protected; the reported data are accurate, complete, and verifiable from the source documents; the equipment used to assess variables in the clinical investigation is maintained and calibrated per manufacturer instructions and Sponsor requirements; and the study is conducted in compliance with the current approved protocol (and amendment[s], if applicable), with current GCP, and with applicable regulatory requirements.

All investigative sites will have a site initiation. Monitoring will be conducted periodically while the clinical study is ongoing. Monitoring methods may include site visits, telephone, written, and fax correspondence. The assigned Clinical Site Manager (CSM) will contact each site at appropriate intervals. The Lead Clinical Site Manager (LCSM) will determine the frequency of site visits. Close-out visits will take place after the last visit of the last subject.

Enrollment will be tracked and reported at regular intervals. Details regarding enrollment (eg, number of subjects pre-screened, screened, reasons for screen failures) may be requested of the investigative site and must be provided within a reasonable time period.

The Sponsor will be responsible for implementing and maintaining quality assurance and quality control systems to ensure the study is conducted and data are generated, documented and reported in compliance with the protocol, GCP and applicable regulatory requirements. The Sponsor will secure agreement from all involved parties to ensure direct access to all study related sites, source data and documents, and reports for the purpose of monitoring and auditing by the Sponsor, and inspection by domestic and foreign regulatory authorities. Quality control will be applied to each stage of data handling to ensure that all data are reliable and have been processed correctly. Agreements made by the Sponsor with the Investigator/Institution and any other parties involved in the clinical study will be provided in writing as part of the protocol or as a separate agreement.

16.5 Regulatory Documentation and Records Retention

The Investigator is accountable for the integrity, retention, and security of all study related data. The Investigator must maintain accurate, complete, and current records relating to the clinical study. The Investigator must maintain the required records during the investigation and for a period of time specified by local law or per the Clinical Study Agreement, whichever is longer. If the Investigator retires, relocates, or for any other reason withdraws from responsibility of keeping the study records, the Sponsor must be notified and suitable arrangements made for retention of study records and source documents needed to comply with national and international regulations.

18 APPENDICES

Not Applicable

Alcon - Business Use Only Protocol - Clinical

Document: TDOC-0052629

Version: 3.0; Most-Recent; Effective; CURRENT

Status: Effective

Effective Date: 04-Apr-2017

**Job Notes:**

This is the original (Version 1.0) Statistical Analysis Plan for this study. This version of the Statistical Analysis Plan is based on Version 1.0 of the study protocol.

**Executive Summary:**

Key objective: to compare the refractive predictability (prediction error) between the Cataract Refractive Suite (CRS) and standard manual technique at 1 month postoperative.

Decision criterion: percentage of eyes in which the Manifest refraction spherical equivalent (MRSE) at 1 month is  $\leq 0.5D$  relative to predicted MRSE when comparing the CRS group with standard manual technique.

## List of Abbreviations

ADE	Adverse device effects
AE	Adverse event
ATC	Anatomical Therapeutic Chemical
[REDACTED]	[REDACTED]
CDE	Cumulative dissipated energy
CI	Confidence Interval
CRS	Cataract Refractive Suite
DBL	Database lock
FAS	Full analysis set
IOL	Intraocular lens
IOP	Intraocular pressure
[REDACTED]	[REDACTED]
[REDACTED]	[REDACTED]
MedDRA	Medical Dictionary for Regulatory Activities
MRSE	Manifest refraction spherical equivalent
[REDACTED]	[REDACTED]
PD	Protocol deviation
PT	Preferred term
SADE	Serious adverse device effects
SAE	Serious adverse event
SAP	Statistical analysis plan
SD	Standard deviation
SOC	System organ class
[REDACTED]	[REDACTED]
[REDACTED]	[REDACTED]
VA	Visual acuity
WHO	World Health Organization

## 1 Study Objectives and Design

[figure not shown]
This statistical analysis plan (SAP) describes the statistical analysis outlined in Section 15 of the study protocol along with any additional analyses, specifications, or deviations from the protocol planned before database lock (DBL).

### 1.1 Study Objectives

The primary objective is to compare the refractive predictability between the CRS and standard manual technique at 1 month post-operative.

Secondary objectives include:

1. To compare the amount of cumulative dissipated energy (CDE) expended in the eye between the CRS and standard manual technique.
2. To assess the average estimated aspiration fluid used during surgery between the CRS and standard manual technique.
3. To assess the average aspiration time spent during surgery between the CRS and standard manual technique.

[figure not shown]

## 1.2 Study Description

This is a prospective, multi-center, observer masked, randomized, active control, contralateral design study. Subjects with bilateral cataracts will be enrolled at approximately 12 investigational sites and undergo cataract surgery.

Subjects will attend 8 planned study visits: a Screening visit from Day -30 to Day -1 followed by 7 visits during an approximate 5-month post-surgery period (see Figure 1-1).

Figure 1-1 Study Design

### **1.3 Randomization**

A member of the Randomization Programming group at Alcon who is not part of the study team will generate the randomized allocation schedule for surgery procedure group. Randomization will be implemented in an Interactive Response Technology system.

### **1.4 Masking**

This is an observer masked study. Site personnel who perform the manifest refraction subjective assessment and visual acuity testing after randomization will remain masked to the procedure group until after the final DBL. The same masking restriction applies to the analysts who perform the interim analysis. Surgery assignment may be known to Alcon, Novartis, and other site personnel. However they will not reveal the surgery assignment to masked site personnel or masked interim analysis team at any time during the study.

### **1.5 Interim Analysis**

This study will initially randomize and treat 300 subjects. An interim analysis will be performed once 200 subjects have been randomized, treated and completed their assessment for the primary effectiveness endpoint at Month 1 (Visit 3A). Additional subjects may be enrolled based on the result of the interim analysis. The study will randomize and treat up to 500 subjects in total.

## **2 Data Analysis General Information**

The statistical software used for the analyses will be SAS version 9.4 or later unless otherwise noted.

Descriptive statistics for continuous variables will include the number of observations, mean, standard deviation (SD), median, minimum, and maximum. .

For categorical variables frequency and percentage will be presented for non-missing data.

### **2.1 General Definitions**

### **2.2 Baseline and Post-baseline**

Baseline date is referred to as Surgery (Day 0) of the study. Note that baseline date is the date of surgery for each eye respectively as each eye is implanted on different days.

Baseline (pre-surgery) value for effectiveness and safety variables is the last available, non-missing, scheduled or unscheduled value collected prior to surgery.

All data collected after Surgery (Day 0) are defined as post-baseline data.

### **2.3 Unscheduled Visits**

All unscheduled visit data will be listed as outlined in their relevant section if applicable.

## **3 Analysis Sets**

### **3.1 Effectiveness Analysis Sets**

The full analysis set (FAS) will contain all eyes that are randomized and for which an IOL is successfully implanted; all eyes in the FAS will be assigned to the surgery procedure actually received for analysis purposes. The FAS will be the primary analysis set for all effectiveness summaries and analyses, as well as all baseline and study summaries (i.e. subject disposition, background and demographic characteristics, medical history).

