15.2 Analysis Data Sets

The full analysis set (FAS) will contain all eyes that are randomized and for which an IOL is successfully implanted; all eyes in the FAS will be assigned to the treatment actually received for analysis purposes. The FAS will be the primary analysis set for all effectiveness summaries and analyses, as well as all baseline and study summaries.

The safety analysis set will contain all eyes for which LenSx is activated and laser cut is started for the test eyes and corneal incision is begun for the control eyes; all eyes in the safety analysis set will be assigned to the treatment actually received. The safety analysis set will be the primary analysis set for all summaries and analyses of safety data.

Assignment of study eyes to the appropriate analysis set(s) will be determined prior to database lock.

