### **3.2 Safety Analysis Set**

The safety analysis set will contain all eyes for which LenSx is activated and laser cut is started for the test eyes and corneal incision is begun for the control eyes; all eyes in the safety analysis set will be assigned to the procedure group actually received. The safety analysis set will be the primary analysis set for all summaries and analyses of safety data.

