## **4 Subject Characteristics and Study Conduct Summaries**

### **4.1 Subject Disposition**

A subject disposition table based on the FAS will be presented that displays the number and percentage of subjects who completed or discontinued the study prematurely including the reason for discontinuation. In addition the total number and percentage of subjects passing and failing screening will be presented for all screened patients. A patient accountability table for subjects with at least one eye in the FAS will be provided based on Table C.1 in ANSI Z80.12-2007.

The number of eyes within each of the analysis sets ([Section 3.1](#) and [Section 3.2](#)) used in the study will be given. The reasons for exclusion from each set will be listed.

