## 5.2 Effectiveness Hypotheses

### 5.2.1 Primary Effectiveness Hypotheses

The primary effectiveness objective is to demonstrate superiority of the CRS compared to standard manual techniques with respect to refractive predictability at Month 1. The following hypotheses will be tested:

$$H_0: p_c \leq p_s$$

$$H_1: p_c > p_s$$

where  $p_c$  and  $p_s$  are the percentage of eyes with manifest refraction spherical equivalent within 0.5D of predicted postoperative spherical equivalent at Month 1 in the CRS and standard manual technique arms respectively.

[figure not shown]

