## 5.3 Statistical Methods for Effectiveness Analyses

All analysis in this section will be based on the FAS.

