### 5.3.1 Primary Effectiveness endpoint

[figure not shown]
The primary effectiveness analysis will be analyzed using a one-sided McNemar's test at the 5% significance level. P-value for the difference in the population proportions will be estimated and presented.

[figure not shown]
The number and percentage of eyes with manifest refraction spherical equivalent  $\leq 0.5D$  of predicted post-operative spherical equivalent will be presented by surgery procedure and visit.

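### The superiority test uses only implanted eyes labelled by the procedure received, and no as-randomised test is visible, so it can favour CRS if departing CRS eyes do worse than their fellow eyes

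*SAP*

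**What the plan says.** Both documents define one effectiveness set. Protocol 15.2 sets the entry condition: "The full analysis set (FAS) will contain all eyes that are randomized and for which an IOL is successfully implanted". It labels eyes by treatment received, and SAP 3.1 repeats the rule: "all eyes in the FAS will be assigned to the surgery procedure actually received for analysis purposes". SAP 5.3 adds: "All analysis in this section will be based on the FAS". The visible text contains no other effectiveness set.

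SAP 5.2.1 gives the purpose: "The primary effectiveness objective is to demonstrate superiority of the CRS compared to standard manual techniques". SAP 5.3.1 gives the test: "The primary effectiveness analysis will be analyzed using a one-sided McNemar's test at the 5% significance level". The secondary one-sided paired t-tests (SAP 5.3.2) use the same set. SAP 5.5 allows no imputation.

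The supporting outputs are descriptive. SAP 4.1 counts the eyes in each set and states: "The reasons for exclusion from each set will be listed". Protocol deviations (SAP 4.2), device deficiencies (6.3.3) and surgical problems (6.3.7) are tabulated and listed. The safety set is also labelled as received: "all eyes in the safety analysis set will be assigned to the procedure group actually received".

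Parts of SAP 5.3.1 are not shown and a heading after 5.3.2 is redacted, so what follows applies to the visible text only.

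**The concern.** Having an IOL implanted and the procedure received are both settled after randomisation, by a surgeon who knows the assignment. McNemar's test needs one CRS eye and one manual eye per subject. A CRS-assigned eye counted as manual leaves two manual eyes; an eye without an IOL leaves no pair. In either case the fellow eye's result is lost too. An implanted eye that stays labelled CRS and misses 0.5 D still counts as a CRS failure, so the problem is confined to eyes that leave.

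The losses need not be symmetric. Protocol 9.4.1 lists incomplete capsulotomy and capsular tear for both techniques, but suction failure for LenSx only. CRS consists of three devices, and the visible text does not say which label an eye takes when only some are used. The laser-start marker in SAP 3.2, "all eyes for which LenSx is activated and laser cut is started for the test eyes", belongs to the safety set. Nor is there a rule for subjects whose two eyes received the same procedure.

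At stake is the 5% error of a one-sided superiority claim, and with it the gate to the secondary tests.

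**Working it through.** **1. The plan's own figure.** Miettinen's approximation, one-sided 5%, 90% power, difference d = 0.83 − 0.75 = 0.08, discordance ψ:

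n = [z₀.₉₅ψ + z₀.₉₀√(ψ² − d²(3+ψ)/4)]² / (ψd²)

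- ψ = 0.21: 266.4, so 267, as stated.
- ψ = 0.33: 432.05, so 433, as stated.

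The calculation treats every pair as one CRS and one manual eye.

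**2. The shift.** Let f be the share of pairs lost because the CRS-assigned eye departed, s the success rate of those eyes and c that of their fellow eyes. The as-randomised difference is (1−f) × (difference in kept pairs) + f(s−c). If it is zero, the kept-pair difference is f(c−s)/(1−f). If a share g of control eyes leaves in the same way, it becomes (f−g)(c−s)/(1−f−g).

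**3. Inputs.** From the plan: manual success 75%, 21% discordance, and 300 subjects less 10% drop-out = 270 pairs. Assumed, because the documents give none of them: f = 2% to 5% (6 to 15 of 300 subjects), s and c. Two cases for c:

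- (a) Departing pairs keep the plan's implied correlation. With 75%/75% and 21% discordance, both eyes succeed in 0.75 − 0.105 = 64.5% of pairs. A fellow eye then succeeds with probability 0.645/0.75 = 0.86 if the CRS eye succeeds and 0.105/0.25 = 0.42 if it fails, so c = 0.42 + 0.44s.
- (b) Upper case: c stays at 75%.

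Example for (a), f = 5%, s = 50%: c = 0.64, and the shift is 0.05 × 0.14/0.95 = 0.74 points.

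**4. One-sided error with no true difference.** McNemar z > 1.645 on 270(1−f) pairs, 1,000,000 simulated trials per cell; the error with no departures is 4.94%.

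| f | s | (a) shift, points | (a) error | (b) shift, points | (b) error |
|---|---|---|---|---|---|
| 2% | 70% | 0.06 | 5.2% | 0.10 | 5.4% |
| 2% | 60% | 0.17 | 5.6% | 0.31 | 6.1% |
| 2% | 50% | 0.29 | 6.1% | 0.51 | 7.1% |
| 5% | 70% | 0.15 | 5.5% | 0.26 | 6.0% |
| 5% | 60% | 0.44 | 6.8% | 0.79 | 8.5% |
| 5% | 50% | 0.74 | 8.2% | 1.32 | 11.7% |

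Exact enumeration of the same test agrees within about 0.3 points; the largest gap is 12.0% against 11.7% in the last cell.

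**5. Where it vanishes, reverses or grows.**

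- c = s, including both at 75%: 5.0%.
- s = 80% under (a): 4.8% (f = 2%) and 4.4% (f = 5%).
- Control eyes leaving at half the CRS rate, s = 50% to 60%: 5.3% to 6.4% under (a), 5.5% to 7.8% under (b). At an equal rate: 5.0%.
- Maximum size (450 pairs, 33% discordance, c = 0.66 + 0.12s), s = 50% to 60%: 6.1% to 10.9% under (a), 6.3% to 12.0% under (b).
- As-randomised test with the departing pairs put back: 4.8% to 5.0%.

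**6. A differently parameterised check.** With 267 pairs, discordance held at 21%, f = 5% and a 20-point shortfall, the shift is 0.05 × 0.20/0.95 = 1.05 points and the error 9.9%. With no shortfall it is 4.95%; if departing eyes do 20 points better it is 2.2%.

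The secondary endpoints cannot be quantified, because the documents give no means or SDs.

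**The case against.** The size rests on assumptions, and the documents give some reason to expect a small gap. A CRS eye completed manually gets the same technique as its fellow, in the same subject, with the same lens model, and the Verion Vision Planner calculation is used for both eyes. That points to s near c, where there is no bias. Case (b) ignores the within-subject correlation that 21% discordance implies. This stands as a limit on size. Eyes that leave because of a complication could still do worse, and nothing in the plan protects against it.

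Whether a pair leaves at all depends on the label. If an eye with failed suction but the other devices used still counts as CRS, its pair stays. A complete swap of both eyes also keeps the pair. Both points are correct, and they are a reason to define the label before the data are seen.

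An eye without an IOL has no prediction error, so part of the restriction is inherent in the endpoint. This is accepted: the labelling rule is the part that can readily be changed.

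Departures would show in the listings, and Protocol 15.2 fixes set membership before database lock. That limits later choice, but SAP 1.4 lets sponsor staff know the assignment, and no listed output gives the endpoint by randomised technique. An as-randomised analysis in the hidden text cannot be ruled out.

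**Conclusion.** The concern holds in its conditional form and should be fixed; confidence is medium. The visible plan tests superiority only in implanted eyes labelled by procedure received, and this favours CRS whenever departing CRS eyes do worse than their fellows and control losses do not offset it. At the initial sample size, under correlation consistent with the plan, the one-sided error is 5.2% to 6.1% at f = 2% and 5.5% to 8.2% at f = 5%, for s between 50% and 70%. With fellow eyes held at 75% it reaches about 12%. It is 5.0% with no gap or with equal losses, and below 5% if departing eyes do better. Since f, s and c are all assumed, this shows an unprotected direction of error and does not predict a large bias.

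**What to change.** **Preferred.** In Protocol 15.2 and SAP 3.1 and 5.3.1, run the primary McNemar test with each eye under its randomised technique, using the observed Month 1 refraction of every eye with an IOL. Keep the as-received FAS test as a sensitivity analysis.

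**Minimum.** Leave the primary test unchanged and pre-specify the as-randomised McNemar test as a sensitivity analysis before database lock.

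In either case:

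- State that pairs lacking a Month 1 result in either eye (missed visit, or second eye not operated) are left out under SAP 5.5 and counted by randomised sequence.
- Add a sensitivity run that scores eyes left without an IOL because of a surgical problem as failures.
- Define, for analysis, what counts as CRS received when only some of the three devices are used, and state that same-procedure pairs leave the as-received test.
- In SAP 4.1, report conversions, same-procedure pairs and exclusions by randomised technique for all randomised subjects.

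**Cost.** The minimum is SAP wording and extra runs of the same test on data already collected. Changing the primary analysis also needs a protocol amendment with IRB/IEC approval, in a study that was already enrolling at Amendment 2.

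It also costs power. Take 83% against 75% in kept pairs and s = c = 75% in departing pairs, starting from 270 pairs. The difference falls from 8.0 points to 0.98 × 8 = 7.8 (f = 2%) or 0.95 × 8 = 7.6 (f = 5%). Power falls from about 89% on the as-received set (89.4% and 88.5%) to 88.5–88.9% (f = 2%) or 85.6–86.9% (f = 5%). With s = 50% to 60% it is 84.5–87.6% or 71.2–82.7%. No added subjects are needed to run the test, but restoring 90% at s = c = 75% would take 278–283 pairs (f = 2%) or 297–310 (f = 5%) against 267. The stated 90% should therefore be described as holding when eyes receive their assigned technique.
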